### **11.2. Sample Size Determination**

Based on previous studies of this intervention(5) and studies in similar populations(3), we estimate an 8-10mmol/mol change in HbA1c at 12 months in the intervention group in those who engage with the programme (SD 8.6mmol/mol), with a 1-2mmol/mol (SD 6mmol/mol) change in the control group. With  $\alpha$  and  $\beta$  set at 0.05 this would require approximately 48 participants; however to power for a co-primary outcome would require 72 to 88 participants in total (allowing for variability in estimated effect size). In similar trials of behavioural interventions we would expect retention to follow up of >80%; allowing for the online nature of this trial, and the retention rates of observational studies of this intervention we will aim to recruit 100 participants to allow for cumulative attrition at the intervention sign-up, engagement, and follow up stages.

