There is a growing support from observational evidence to suggest that remote support via a digital platform can positively affect the weight and glycaemia of patients with type 2 diabetes who engage with these interventions. One such platform offering remote behavioural and dietary support for people with type 2 diabetes provides a three-month remote behavioural change programme with mentoring from a registered dietitian or nutritionist (health coach), encouraging adoption of a low energy, low-carbohydrate diet, peer group support, structured education articles and activity tracking technology. These elements are accessed via a smartphone or web-based application; each participant additionally receives an instructional handbook, and recipe book (+/-wireless weighing and activity tracking technology). A service evaluation of 190 participants referred as part of routine care from January to July 2018 found that 75% of patients (n=144) started the programme, and 65.3% (94) of these submitted weight readings after 12 months. Of these, 60% achieved over 5% total body weight loss, and 28.7% achieved over 10% body weight loss; the average total 12 month weight change was -7.8kg (+/- 8.6kg). 28.5% of participating patients attended for a blood test with their GP after 12 months as part of routine care; in those with available HbA1c data, there was a statistically significant change in HbA1c compared to baseline (mean -10.4mmol/mol, SD +/- 8.6mmol/mol)(5). An earlier larger cohort of 896 patients who completed a similar programme (3 months of “core” support, plus ongoing access to sustainable advice and encouragement of weekly engagement) over a 1 year period, comprising both self-funded clients and those referred by their GP free of charge, found a significant change in mean weight of -7.12kg (SD 6.37kg) at 6 months and -6.14kg (SD 9.97 kg) at 12 months compared to baseline measures(6). While the weight and glycaemic changes reported appear promising, and clinically significant, these observational studies have several key limitations (including the generalisability of the patient population (a selected group of people with high intrinsic motivation to take part, often in locally limited geographical areas); observational design and lack of a control or comparator group; and significant loss to follow up and absence of follow up data, without the ability to determine why) that preclude drawing reliable conclusions as to the programme’s performance and effectiveness.

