## **9.8. Early Discontinuation/Withdrawal of Participants**

Each participant has the right to withdraw from the trial at any time.

During the course of the study a participant may choose to withdraw early from the study treatment at any time. This may happen for several reasons, including but not limited to:

- The occurrence of what the participant perceives as an intolerable AE.
- Inability to comply with study procedures
- Participant decision

Participants may choose to stop treatment and/or study assessments but may remain on study follow-up.

Participants may also withdraw their consent, meaning that they wish to withdraw from the study completely. If a participant decides to withdraw from treatment, we will seek to retain them in the trial for follow-up by explaining the value to the trial of collecting follow up data from all participants by speaking with the participants. However, if the participant wishes to withdraw from follow up we will use their data up to the point that they withdraw unless they request that we do not do so. The reason for withdrawal will be recorded in the electronic case report form (ECRF). Participants that withdraw from the trial will not be replaced. Should a participant wish to withdraw, their information that is held with the provider, will be retained for 10 years following cease of use. This relates to information provided to the intervention provider by the study team and the participant. Cease of use refers to the last login to the online programme by the participant. Each participant can request that their personal information that is retained by the intervention provider is deleted by contacting either the intervention provider or the study team, who will process that request.

In addition, the Investigator may discontinue a participant from the study treatment at any time if the Investigator considers it necessary for any reason including, but not limited to:

- Pregnancy
- Ineligibility (either arising during the study or retrospectively having been overlooked at screening)

- Significant protocol deviation
- Clinical decision

The type of withdrawal and reason for withdrawal will be recorded in the CRF.

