### **11.1. Description of the Statistical Methods**

The primary statistical analysis of efficacy outcomes will be carried out on the basis of intention-to-treat (ITT). This is, after randomisation, participants will be analysed according to their allocated intervention group irrespective of what intervention they actually receive. We will endeavour to obtain full follow-up data on every participant to allow full ITT analysis, but we will inevitably experience the problem of missing data due to withdrawal, loss to follow up, or non-response to questionnaire items.

We will analyse the primary continuous outcome with a linear model adjusting for baseline value of the relevant variable where relevant. For exploratory analyses, we will use analogous models, but interpret the data in an exploratory manner rather than confirmatory. For binary outcomes (e.g. remission), we will test for a difference in proportions, e.g. using Fischer's exact test.

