### **11.3. The Level of Statistical Significance**

The results from the trial will be prepared as comparative summary statistics (difference in proportions or means) with 95% confidence intervals. All the tests will be done at a 5% two-sided significance level.

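### The sample size uses the HbA1c effect expected in people who engage, but the primary analysis is ITT; non-engagement is budgeted as attrition when it dilutes the effect

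*Combined protocol and SAP*

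**What the plan says.** Section 11.2 (Sample Size Determination) gives the planning effect as "we estimate an 8-10mmol/mol change in HbA1c at 12 months in the intervention group in those who engage with the programme (SD 8.6mmol/mol"). For the comparator arm it assumes that HbA1c moves by 1 to 2 mmol/mol, SD 6. With alpha and beta "set at 0.05 this would require approximately 48 participants". It then gives 72 to 88 in total for the co-primary outcome, expects retention above 80%, and concludes: "we will aim to recruit 100 participants to allow for cumulative attrition at the intervention sign-up, engagement, and follow up stages".

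Section 11.1 makes the primary analysis intention-to-treat: "participants will be analysed according to their allocated intervention group irrespective of what intervention they actually receive". Section 9.8 adds: "If a participant decides to withdraw from treatment, we will seek to retain them in the trial for follow-up". Section 11.3 sets the test level: "All the tests will be done at a 5% two-sided significance level".

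The plan assumes no engagement rate and states no ITT effect. The nearest evidence is the service evaluation in section 5, which also reports the SD of 8.6. It "found that 75% of patients (n=144) started the programme, and 65.3% (94) of these submitted weight readings after 12 months".

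**The concern.** Someone randomised to the app who never signs up, or stops using it, does not leave an ITT analysis. If that person attends the 12-month visit, the result counts in the intervention arm. Only a missing outcome reduces the number analysed; non-engagement reduces the mean difference.

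The two need different allowances. Attrition at retention rate r is met by dividing N by r. Dilution to a share e of the effect requires N to grow roughly as 1/e², so an allowance built for attrition is too small for the same percentage of non-engagement.

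At stake is how the result is read. A null ITT result could be taken as coming from a trial with 95% power when its power against the plan's lower effect values is clearly less.

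**Working it through.** **Inputs.** Engager change 8–10 (SD 8.6) and control change 1–2 (SD 6), section 11.2. The engager contrast D therefore runs from 8 − 2 = 6 to 10 − 1 = 9. Allocation 1:1 (section 7); two-sided 5% (section 11.3); power 95% (section 11.2). Retention 80%, the floor of the plan's expectation, gives 100 × 0.80 = 80 analysed, 40 per arm.

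**Reproducing 48.** With D = 8, the normal approximation gives (1.96 + 1.645)² × (8.6² + 6²)/8² = 22.3, so 23 per arm (46). The noncentral-t calculation gives 24 per arm, **48** in total, exactly the plan's figure. It uses the full engager contrast with no dilution. At D = 6 the same method gives 82.

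**Dilution model (assumption).** A share e of the intervention arm engages and the rest change like controls:

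- ITT difference = e × D
- intervention-arm variance = e × 8.6² + (1 − e) × 6² + e(1 − e) × D²
- power from the noncentral t with Welch degrees of freedom, control SD 6

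**Worked case, D = 8, e = 0.75.** ITT difference = 6.0. Variance = 55.47 + 9.00 + 12.00 = 76.47, SD 8.74. With 40 per arm, SE = √((76.47 + 36)/40) = 1.68 and power is 94%. For 95% power, 84 must be analysed. Treating the same non-engagement as attrition would give 48/0.75 = 64, and 64 analysed give 88% power. The plan does not itself do this division; it only shows why the two allowances are not interchangeable.

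**Worked case, D = 6, e = 0.75.** ITT difference = 4.5. Variance = 55.47 + 9.00 + 6.75 = 71.22, SD 8.44, SE = 1.64, power 77%.

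**Power with 80 analysed:**

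| Engagement | Alpha | D = 6 | D = 7 | D = 8 | D = 9 |
|---|---|---|---|---|---|
| 85% | 0.05 | 86% | 94% | 98% | 99% |
| 75% | 0.05 | 77% | 88% | 94% | 98% |
| 85% | 0.025 | 79% | 90% | 96% | 99% |
| 75% | 0.025 | 68% | 81% | 90% | 95% |

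The 75% is the start rate in section 5 (144/190 = 75.8%); 85% is a more favourable assumption. The 0.025 rows apply only if alpha is split between the two co-primaries, which the plan does not state. As a low stress value, 49% engagement (94/190 = 49.5% returned 12-month weights, a measure that mixes data return with engagement) gives 45%, 56%, 66% and 74% at alpha 0.05.

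**Total analysed needed for 95% power, alpha 0.05:**

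| Engagement | D = 6 | D = 7 | D = 8 | D = 9 |
|---|---|---|---|---|
| 100% | 82 | 62 | 48 | 38 |
| 85% | 112 | 84 | 66 | 54 |
| 75% | 140 | 106 | 84 | 70 |

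**Engagement needed for 95% power with 80 analysed.** At alpha 0.05: 87%, 77% and 69% for D = 7, 8 and 9. At D = 6, power is 94.6% even with full engagement. At alpha 0.025: 94%, 83% and 75% for D = 7, 8 and 9.

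**The count itself.** Eighty analysed covers 72 but not 88. Reaching 88 needs 88% retention of 100, or 88/0.80 = 110 recruits.

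**Detectable ITT difference with 80 analysed (SDs 8.6 and 6).** 4.7 at 80% power and 6.1 at 95% (alpha 0.05); 5.2 and 6.6 at alpha 0.025.

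**The case against.** The strongest reply is that 100 is large enough in practice. At D = 8, the contrast behind 48, and 75% engagement, the 84 needed lies inside the plan's 72–88. Power with 80 analysed is 94%, and retention is expected to exceed 80%; with 84 analysed power is 95%. At the midpoint of the range, D = 7.5, power is 91.5% at 75% engagement and 96.5% at 85%.

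The dilution model may also be harsh:

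- Non-engagers are still allocated a medication-review call, a handbook and a recipe book. If they gain 2 mmol/mol over controls (an assumption), power at 75% engagement is 87%, 94%, 97% and 99% for D = 6 to 9.
- If baseline HbA1c correlates 0.3–0.5 with change (an assumption), the planned adjustment lifts power at D = 6 and 75% engagement to 81–88%.
- If loss to follow-up falls mainly on non-engagers, the analysed sample is more engaged.
- Participants must want to change diet or lifestyle and must complete online questionnaires before randomisation, so engagement may exceed that of routine referrals.

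Much of this stands as a limit on the consequence: the target of 100 is not shown to be too small in every case. It does not rescue the stated rationale. The documents give no engagement rate, non-engager effect or baseline correlation. Loss concentrated in non-engagers would bring a missing-data problem of its own. The 72–88 range allows for uncertainty in effect size, without mentioning engagement or showing its derivation. Where 100 suffices, it does so through allowances made for other reasons.

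**Conclusion.** The concern holds. The alpha = beta = 0.05 calculation describes an engager contrast, the primary analysis estimates an ITT contrast, and section 11.2 treats the difference between them as attrition. With 80 analysed and 75–85% engaging, power for one outcome at two-sided 5% is 94–98% at a contrast of 8 but 77–86% at 6 and 88–94% at 7, all within the plan's own range. A split alpha lowers these further.

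The figures assume that non-engagers change like controls, that loss to follow-up is unrelated to engagement, and that baseline adjustment earns no credit. That the mismatch exists does not depend on those assumptions; its size does. The validity of the ITT estimate and its confidence interval is unaffected. The rationale should be corrected; the design need not change.

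**What to change.** Keep N = 100 and restate section 11.2 on the ITT contrast, at whatever alpha is chosen for the co-primaries. Possible text at two-sided 5%:

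> With 80 of 100 participants analysed (80% retention), the detectable ITT difference in HbA1c change is 4.7 mmol/mol at 80% power and 6.1 at 95% power (SDs 8.6 and 6). If 75–85% of the intervention group engage and the remainder change as controls do, power is 77–86%, 88–94%, 94–98% and 98–99% for engager contrasts of 6, 7, 8 and 9 mmol/mol.

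If alpha is split to 0.025, the detectable differences become 5.2 and 6.6, and the power figures should come from the 0.025 rows of the table.

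Confine the attrition allowance to missing outcomes, and describe non-sign-up and non-engagement as dilution. If 72–88 is retained, show how it was derived and on which contrast, and note that 80 analysed reaches 72 but not 88.

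The cost is wording in section 11.2 and a less favourable power statement at the lower end of the effect range. No extra participants are needed, and the primary analysis and trial conduct are unchanged.

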### **11.3. The Level of Statistical Significance**

The results from the trial will be prepared as comparative summary statistics (difference in proportions or means) with 95% confidence intervals. All the tests will be done at a 5% two-sided significance level.

## **12. DATA MANAGEMENT**

The data management aspects of the study are summarised here with details fully described in the Data Management Plan.

### **12.1. Access to Data**

Direct access will be granted to authorised representatives from the Sponsor and host institution for monitoring and/or audit of the study to ensure compliance with regulations.

### **12.2. Data Recording and Record Keeping**

The trial is being run with support from the PC-CTU. The data management will be run in accordance with the Trials Unit SOPs, which are fully compliant with Good Clinical Practice (GCP). A trial specific Data Management Plan (DMP) will be developed for the trial outlining in detail the procedures that will be put in place to ensure that high-quality data are produced for statistical analysis.

A unique trial specific number and/or code in any database will identify the participants. All data will be directly entered online by the participant unless followed- up by the research team, using phone calls,

text messages or email. There will be two databases as all information is collected online and therefore identifiable information is also collected. Only the trial team will be able to have access to the databases. Trial data will be kept in compliance with the relevant Sponsor's policy, in particular: the University of Oxford: Data Protection Checklist: <https://researchsupport.admin.ox.ac.uk/policy/data/checklist> and Practical: Consideration: <https://researchsupport.admin.ox.ac.uk/policy/data/practical>

The data will be stored in Sentry and REDCAP and both are held on University secure servers and the University IT team provide security through Firewalls and backups of the systems are taken daily.

The trial management file and any paper CRFs (if used) will be secured in a locked cabinet in a locked room in the Department of Primary Care Health Sciences.

On completion of the trial and data cleaning, the trial documentation will be transferred to a secure, GCP compliant archiving facility, where they will be held for five years. Participants' identifiable information will be destroyed at the end of the trial. Prior to database lock, the Data Manager will undertake a dataset review. The anonymised dataset will be stored on a University secure server with access held by the Senior Data Manager. Procedures in relation to data transfer are documented within the PC-CTU\_SOP\_DM108 and in accordance with the Information Governance Policy.

The audio recordings of telephone interviews will be stored in password protected files, saved under a file name of participant ID and no other personally identifiable information, on a secure server. The audio recordings will be transcribed by an approved University transcriber with whom appropriate information security and confidentiality agreements are in place. File transfer (of initial audio and then transcriptions) will take place using encrypted files and a University IG approved method of data transfer (Oxfile), with encryption password sent separately and to a different address. Transcriptions will be pseudonymised as soon as is practical, and original audio recordings deleted as soon as the transcriptions have been cross checked and the original audio is no longer required. Pseudonymised transcriptions will then be stored in a file on a secure server.

For those who are assigned to the intervention group, participants' contact information (name and email), with consent, will be passed to Second Nature using a secure, encrypted NHS email. All other identifiable information, which will be provided by the participant to Second Nature, is governed by their privacy policy (available at: [secondnature.io/terms](http://secondnature.io/terms)). The provider, Second Nature, will retain any information held on an individual for up to 10 years after that individual has ceased use of the System. At that point, the information will be deleted. As covered in section 5 of the providers' privacy policy, participants may request that personal information is deleted at any time. This referral pathway mirrors how this process would work in a real world setting and replicates the current referral pathway to Second Nature. Data on participant engagement with the app will be received from the company under appropriate agreements. These data will include (as examples) measures of engagement with the three main components of the programme: Learn, Track, and Support. "Learn" interactions are defined as the number of articles read by participants; "Track" interactions are defined as the number of times a participant registered or viewed weight readings; "Support" interactions are defined as the number of messages sent or read in either the private or group chat channels. This data will be pseudonymised.

The participant food diaries will be collected using gold standard dietary analysis programme Intake24, a web-based 24 hour dietary recall system. This system is used for the government-run National Diet and Nutrition Survey and is the best available method to collect this data. The Third Party, Intake24, has been assessed by the Information Security team at Oxford University, via a Third Party Security Assessment, to present a low risk for collection of data of this nature and scale, and is on the IG approved list of third

parties, and all necessary agreements will be in place for use of this third party. Participants will be sent a PID-specific link to complete their dietary recall data; this link will be sent by email by the research team (in compliance with all University policies regarding email). Participants will not upload any personal data to this platform, it is solely to capture their dietary intake (i.e. what they had to eat and drink in the preceding 24 hours).

### **13. QUALITY ASSURANCE PROCEDURES**

The trial will be conducted in accordance with the current approved protocol, GCP, relevant regulations and standard operating procedures.

Regular monitoring will be performed according to GCP. Data will be evaluated for compliance with the protocol and accuracy in relation to source documents. Following written standard operating procedures, the monitors will verify that the clinical trial is conducted and data are generated, documented and reported in compliance with the protocol, GCP and the applicable regulatory requirements.

A Trial Management Group (TMG) will provide oversight of all matters relating to participant safety and data quality. The study is not blinded, carries low risk with no rules for early termination and the trial protocol would not be modified based on interim data. Therefore it is felt that it is neither necessary nor appropriate to have a specific Data Monitoring and Ethics Committee in addition to the TMG.

A Trial Steering Committee (TSC) will be formed to provide external oversight of the study and its progress.

### **14. PROTOCOL DEVIATIONS**

A study related deviation is a departure from the ethically approved study protocol or other study document or process (e.g. consent process or administration of study intervention) or from Good Clinical Practice (GCP) or any applicable regulatory requirements. Any deviations from the protocol will be documented in a protocol deviation form and filed in the study master file.

### **15. SERIOUS BREACHES**

A “serious breach” is a breach of the protocol or of the conditions or principles of Good Clinical Practice which is likely to affect to a significant degree –

- (a) the safety or physical or mental integrity of the trial subjects; or
- (b) the scientific value of the research.

In the event that a serious breach is suspected the Sponsor must be contacted within 1 working day. In collaboration with the C.I., the serious breach will be reviewed by the Sponsor and, if appropriate, the Sponsor will report it to the approving REC committee and the relevant NHS host organisation within seven calendar days.

## **16. ETHICAL AND REGULATORY CONSIDERATIONS**

This study involves no identified significant risks to participants. They are primarily consenting to engaging with dietary and behavioural advice which is intended to support them to lose weight and improve their diabetes control and general health. There are known no significant risks of this advice.

Venepuncture for blood samples may cause momentary discomfort. Standard NHS operating procedures as used in routine clinical care will be used for the collection and processing of samples, and all will be carried out by appropriately trained clinicians in the participants' usual GP practice.

